8.4 Reporting

Any serious adverse reaction/event not covered in the secondary outcomes (defined in 7.2 and 8.2) adjudicated to be related to the trial intervention by the investigator, will be reported within 24

The CLASSIC trial protocol Page 27/82

hours to the Sponsor or his delegate. If deemed a SUSAR by the Sponsor, he will report it to the Danish Medicine Agency within 7 days after the report of a life-threatening or fatal SUSAR. No later than 8 days after the reporting, the Sponsor will inform the Danish Medicines Agency of relevant information on the Sponsor's and the investigator's follow-up action to the life-threatening or fatal SUSAR. Any other SUSARs will be reported to the Danish Medicines Agency no later than 15 days from the time when the Sponsor is informed.

Once a year, the Sponsor will submit a list of all SARs that have occurred at all sites during the trial period and a report on safety of the trial subjects to the Danish Medicines Agency.

The Sponsor will notify the Danish Medicines Agency when the trial has been completed (no later than 90 days thereafter) and if earlier than planned, the reasons for stopping the trial.

In addition, we will report all SAEs and SARs defined in 7.2 and 8.2 as outcome measures and all SUSARs in the final trial report and the results of the trial will be reported on EudraCT.

9 Procedures, assessments and data collection

9.1.1 Screening

All patients admitted to, or planned for clinical reasons to be admitted to a participating ICU with septic shock will be eligible for screening.

9.1.2 Procedures for informed consent

Participants will be enrolled after consent by proxy is obtained according to national regulations. The procedure for each participating country will be described; that for Danish participants is described in Appendix 5. The Swedish procedure for consent and specific Swedish regulations are described in Appendix 5.1.

9.2 Data collection

9.2.1 Methods

Data will be obtained from the participant's hospital files and national/regional/hospital registers (source data as defined per site, region and country) and by participant survey/interview and entered in the web-based eCRF by trial investigators or their delegates. For participants transferred from a trial ICU to a non-trial ICU, data related to the outcomes will be collected according to national practice e.g. investigator contact to the non-trial ICU or health care registers.

9.2.2 Timing

All variables are defined in Appendix 2.

Baseline variables:

- Sex
- Date of birth

The CLASSIC trial protocol Page 28/82

- Date of admission to hospital
- Date and time of admission to ICU
- From where was the participant admitted to ICU
 - o Emergency department or directly from the pre-hospital setting
 - Hospital ward
 - Operating or recovery room
 - Another ICU
- Focus of infection:
 - o Pneumonia
 - o Gastrointestinal infection
 - Urinary tract infection
 - Skin or soft tissue infection
 - Other
- Co-morbidities:
 - o Active hematologic cancer
 - History of metastatic carcinoma
 - History of ischemic heart disease or heart failure
 - History of chronic hypertension
 - o Chronic dialysis
- Blood values, interventions and vital parameters:
 - Participant weight
 - o Highest plasma lactate value within the last 3 hours of randomisation
 - Highest dose of noradrenaline within the last 3 hours of randomisation
 - o Volumes of IV fluid within the last 24 hours of randomisation
 - o Use of systemic corticosteroids in the last 24 hours of randomisation
 - Highest plasma creatinine value within the last 24 hours of randomisation
 - Use of acute renal replacement therapy in the last 3 days prior to randomisation
 - Habitual plasma creatinine value prior to current hospitalisation (mark estimated or measured)
- Values for the Simplified Mortality Score (SMS score)[43] at ICU admission not covered by the above:
 - Lowest measured systolic blood pressure in the last 24 hours prior to randomisation
 - Respiratory support within the last 24 hours of randomisation (support during surgery excluded)

Daily during ICU admission (day form):

- Fluid input and output
 - Total volume and specific type of IV isotonic crystalloids (isotonic saline and buffered solutions: Ringer's lactate, Ringer's acetate and PlasmaLyte™)
 - o Total volume of other IV fluids
 - Total volume of albumin
 - Total volume of fluids with medications
 - Total volume of fluids with nutrition
 - Total volume of blood products

The CLASSIC trial protocol Page 29/82

- Urinary output on this day (ml)
- Total volume of other losses on this day including drainage, aspirates, stools and bleeding
- Did a major protocol violation occur on this day?
- Use of infusion of vasopressor or inotrope on this day
- Use of systemic corticosteroids on this day
- Use of mechanical ventilation on this day
- Use of renal replacement therapy on this day
- Plasma concentration of creatinine
- SAEs on this day (y/n for everyone)
 - Cardiac ischemic event
 - Cerebral ischemic event
 - Intestinal ischemic event
 - o Limb ischemia
- SARs on this day (y/n for everyone)
 - o General tonic-clonic seizures
 - Anaphylactic reactions
 - Central pontine myelinolysis.
 - Severe hypernatremia
 - Severe hyperchloraemic acidosis
 - Severe metabolic alkalosis

ICU discharge form:

- Died in ICU
- Discharged to the ward at the same or another hospital
- Discharged to another ICU participating in CLASSIC
- Discharged to another ICU not participating in CLASSIC
 - Number of days of infusion of vasopressor or inotrope in this ICU
 - Number of days of mechanical ventilation in this ICU
 - Number of days of renal replacement therapy in this ICU

Follow-up 90 days after randomisation:

- Death (y/n, if yes date of death)
- Date of the last session of any renal replacement therapy
- Date of discharge from hospital
- Additional hospital admissions

Follow-up 1 year after randomisation

- Death (y/n, if yes date of death)
- EQ-5D-5L and EQ-VAS scores
- MoCa scores

The CLASSIC trial protocol Page 30/82

9.3 Data management

The data manager at CTU or his/her delegate will construct and oversee the eCRF. He/she will, as the only person, have access to the randomisation list during trial. The eCRF and the trial database will be hosted at the server of CTU with appropriate back-up and security as per the GCP regulative.

9.4 Confidentiality

Each participant will receive a unique trial identification number. Trial investigators will receive a personal username and passwords to access the randomisation system and the eCRF. Each site will only have access to site specific participant data. Data will be handled according to the National Data Protection Agency and protected by the Danish national laws 'Loven om behandling af personoplysninger' and 'Sundhedsloven'.

9.5 Collection, handling, storage and transportation of human biological material

No additional sampling of human material will be done in the main trial as data entry will rely on routine testing done in the clinical setting. In sub-studies, blood tests will likely be taken in addition to the routine clinical tests. If so, specific protocols will be submitted for approval, as described in section 12.4.

9.6 Access to data

All original records (incl. consent forms, eCRFs, and relevant correspondences) will be archived for 15 years. De-identified data will be made publicly available 9 months after the publication of the outcome data according to the recent ICMJE recommendations [69]. As it is for all CRIC trials, all trial-related documents will be public available at www.CRIC.nu including those of the site master file, the eCRF template, instructions, educational material etc.

10 Statistical plan and data analysis

The analyses will be done according to the principles stipulated in ICH-GCP guidelines [42] and the detailed statistical analysis plan, which will be published before the randomisation of the last participant.

10.1 Sample size and power

10.1.1 Sample size estimation

By enrolling 1554 (2 x 777) participants, we can show a 15% relative risk reduction (7% absolute) in the restrictive group from an estimated 45% 90-day mortality in the standard care group (data from our previous CLASSIC pilot, TRISS and 6S trials [2, 3, 5], systematic reviews [23, 44] and a recent large cohort study [4]) at type 1 and 2 error levels of 5% and 20% (power=80%), respectively.

The CLASSIC trial protocol Page 31/82

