- Experimental intervention. In the IV fluid restriction group no IV fluids should be given in the ICU unless extenuating circumstances occur, including signs of severe hypoperfusion, overt fluid loss or a failing GI tract with a total fluid input of less than 1 L per day. In these circumstances, IV fluid may be given in measured amounts.
- Control intervention. In the standard care group there will be no upper limit for the use of IV fluids.
- Outcomes. The primary outcome is 90-day mortality; secondary outcomes are serious adverse events in the ICU (ischemic events or severe acute kidney injury); days alive without life support at day 90; days alive and out of hospital at day 90 and mortality, health-related quality of life and cognitive function at 1-year.
- Trial size. We will randomise 1554 participants to allow the detection of a 15% relative risk reduction (7% absolute) in the restrictive vs. standard care group in 90-day mortality with a power of 80%.
- Timeline.
 - Primo 2018 Authority approvals in DK
 - Medio 2018 1st participant randomised in DK and authority approvals elsewhere
 - Primo 2019 1st interim analysis
 - Medio 2019 2nd interim analysis
 - Ultimo 2019 3rd interim analysis
 - Medio 2020 Last participant randomised
 - Ultimo 2020 Primary report on 90-day outcomes submitted.
 - Medio 2021 Last participant followed for 1 year
 - Ultimo 2021 Long-term outcome report submitted

The CLASSIC trial protocol Page 2/82

Administrative information

Sponsor

[name], senior staff specialist and professor in intensive care medicine Dept. of Intensive Care
Rigshospitalet
[name]
2100 Copenhagen Ø
[contact]
[contact]

Clinical trial sites

In Denmark

Dept. of Intensive Care Rigshospitalet [name] 2100 Copenhagen Ø

Dept. of Anaesthesia and Intensive Care Bispebjerg Hospital, University of Copenhagen 2200 Copenhagen N

Dept. of Anaesthesia and Intensive Care Herlev Hospital, University of Copenhagen 2730 Herlev

Dept. of Anaesthesia and Intensive Care North Zealand Hospital, University of Copenhagen 3400 Hillerød

Intensive Care Unit Q-022GE Gentofte Hospital 2900 Hellerup

Dept. of Anaesthesia and Intensive Care Zealand University Hospital, Køge 4600 Køge

Dept. of Anaesthesia and Intensive Care Zealand University Hospital, Roskilde 4000 Roskilde

Dept. of Anaesthesia and Intensive Care Slagelse Hospital 4200 Slagelse

Dept. of Anaesthesia and Intensive Care Randers Hospital 8930 Randers

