1.1 The participant population - patients with septic shock

Septic shock is common and often lethal [1]. The WHO estimates that 6.000.000 patients die of sepsis every year and have declared sepsis a global health priority [1]. Patients with septic shock have 90-day mortality rates around 40% to 50% even in the developed part of the world [2, 3, 4, 5]. Many survivors get readmitted to hospital and have impaired health-related quality of life (HRQoL) [6] and struggle with long-term reduced cognitive function [7]. Sepsis care is, therefore, associated with high use of resources in the developed part of the world [8].

Septic shock is defined as the need for vasopressor therapy and elevated lactate levels related to an infection and most often other organ systems are also impaired, including the brain, lungs and kidneys [9]. The most frequent sources of infection in patients with septic shock are pneumonia and abdominal, urinary tract, and soft tissue infections [10, 2, 3, 4].

Taken together, any improvement in sepsis care will result in reduced suffering among patients and relatives and improved global health [1].

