10.2 Statistical methods

The analyses will be done in the intention-to-treat (ITT) population defined as all randomised participants for whom there is consent for the use of data. We will perform the primary analyses adjusted for the stratification variables [45] and challenge the primary result in analyses adjusted for important baseline risk factors (co-morbidities, higher SMS score, and focus of infection (other foci vs. urinary tract infection)[43, 46] and use of corticosteroids, which may reduce the time in ICU and thus the time exposed to the protocol [47]) and analyses of subgroups (Table 2) and the per-protocol population being the ITT population except those having one or more major protocol violations as defined below (Table 3). If there is more than 5% missing data for outcomes and/or covariates, we will impute the missing data using multiple imputations as described below (10.2.4).

All analyses will be 2-tailed and we will use Fisher's exact test for unadjusted comparisons of dichotomized outcomes (mortality at 90-days and 1-year, SAEs and SARs) and logistic regressions for adjusted analyses of these outcomes. The remaining secondary outcomes are continuous measures; we expect that these are highly skewed (non-normally distribution), because of inflation of specific values such as zero for days alive outside hospital for all patients who die while at the ICU. We will use statistical methods that can accommodate this type of data; the precise models will be specified in the detailed statistical plan.

Several of the secondary outcome measures are composite; we will also analyse each component of these outcomes as recommended [42]; the precise models will be specified in the detailed statistical plan.

Table 2. Heterogeneity of the intervention effects on the primary outcome will be analysed in the following subgroups based on baseline characteristics

Subgroup	Definition	Expected direction of	Statistical test
		the interaction	
Participants who are mechanically ventilated	Invasive mechanically ventilated (yes/no)	Larger effect of fluid restriction in mechanically ventilated participants	Test of interaction in the adjusted analysis described above; P- value 0.01

The CLASSIC trial protocol Page 32/82

Participants with	KDIGO (creatinine)	Larger effect of fluid	Test of interaction in
severe acute kidney	criteria of 2 or above	restriction in acute	the adjusted analysis
injury	[41] (yes/no)	kidney injury	described above; P-
			value 0.01

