In any multiple imputation, we will use all relevant outcomes and the stratification variables (site and metastatic or hematologic cancer), SMS-ICU¹⁴ at baseline, site of infection at baseline, comorbidities at baseline (ischemic heart disease or heart failure, chronic hypertension or chronic RRT), use of corticosteroids at baseline, mechanical ventilation at baseline, highest p-creatinine 24 hours prior to randomisation, habitual p-creatinine, p-lactate at baseline, participant weight at baseline, and volume of IV fluids given prior to randomisation. Multiple imputation will be performed separately in the two intervention groups before pooling the full dataset, and the primary result of the trial will be based on these data. The unadjusted, non-imputed analysis will also be presented. If multiple imputation is used, we will also include a best-worst worst-best case scenario to assess the potential impact of any pattern of missingness including that data are 'missing not at random' (MNAR criterion). In the 'best-worst-case' scenario it is assumed that all participants lost to followup in the experimental group e.g. have survived; and that all patients with missing outcomes in the control group have not survived. Conversely, in the 'worst-best-case' scenario, it is assumed that all participants who were lost to follow up in the experimental group have had a harmful outcome; and that all those lost to follow-up in the control group have had a beneficial outcome. When continuous outcomes are used, a 'beneficial outcome' will be defined as the group mean plus two

standard deviations (SD) of the group mean or highest possible value whichever is smallest, and a 'harmful outcome' will be defined as the group mean minus two SD of the group mean or lowest possible value whichever is highest.

General analytical principles

The analyses will be done in the intention-to-treat (ITT) population defined as all randomised participants for whom there is consent for the use of data. The conclusion of the trial will be based on the ITT analysis.

The per-protocol population is defined as the ITT population except those having one or more major protocol violations.

Statistical analyses

Primary outcome

Four analyses will be performed for the primary outcome:

Primary analysis:

1. Logistic regression analysis adjusted for the stratification variables¹⁵ (site and hematologic malignancy /metastatic cancer) in the ITT population. P-values will be two-tailed

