Generalised linear model or nonparametric test stratified for site in the ITT population For the generalised linear model we will initially use Poisson distribution, alternatively negative binomial.¹⁸ If the assumptions for Poisson distribution or negative binomial distribution are not met, data will be analysed using the nonparametric Van Elteren test adjusted for site, but no other variables.¹⁹

The following secondary outcome measures are composite; SAEs, SARs, days alive at day 90 without life support. We will report each component of these outcomes in an appendix to the primary publication without P-values due to the lack of adjustment for multiple comparisons. We will report absolute and relative risk ratios with 99% CIs for dichotomous secondary outcomes. For continuous secondary outcomes we will report mean differences with 99% CIs if they are normally distributed and medians with 99% percentile-based bootstrapped CIs for non-normally distributed continuous secondary outcomes (P-value 0.01) due to the multiplicity of these. A detailed definition of the level of significance for the secondary outcomes is available in the supplement to the published statistical analysis plan. ¹

Sample size

Primary outcome

We plan to enrol 1554 (2 x 777) patients to be able to show a 15% relative risk-reduction (RRR) (7% absolute) in the restrictive group on the primary outcome from an estimated 45% 90-day mortality in the standard care group at type 1 and 2 error levels of 5% and 20% respectively, corresponding to a number needed to treat (NNT) of 14 or less. The anticipated relative risk reduction of mortality and the estimated mortality in the control group is based on data from previous RCTs and systematic reviews.^{20–24}

Trial sequential analysis of existing trials (n=8) have shown that less than 15% of the required information size of 3956 patients to detect or reject a 15% RRR in all-cause mortality with lower versus higher fluid volumes has been reached.²⁵

Secondary outcomes

We expect to have the following statistical power for the secondary outcomes based on 2 x 777 participants, a type 1 error level of 1% and a RRR of 15% in the fluid restriction group versus standard care group:

- 50% power for the number of participants with one or more SAEs (control event rate 25% ^{21,22})
- 10% power for the number of participants with one or more SARs (control event rate 5%^{21,22})

- 80% power for the mortality at 1-year (control event rate 55%^{21,22})

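### 2 x 777 gives 80% power for a 7.0-point reduction (45% vs 38.0%, 15.6% relative), but about 77% unadjusted for the exact 15% relative reduction printed as the same effect

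*Protocol*

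**What the plan says.** Protocol section 10.1.1 states: "By enrolling 1554 (2 x 777) participants, we can show a 15% relative risk reduction (7% absolute" in its bracket, "from an estimated 45% 90-day mortality in the standard care group", "at type 1 and 2 error levels of 5% and 20% (power=80%), respectively". The Trial size item of the protocol abstract says the same: "We will randomise 1554 participants to allow the detection of a 15% relative risk reduction (7% absolute" in its bracket, with 80% power. The SAP, under Sample size, Primary outcome, plans the same 1554 patients "to be able to show a 15% relative risk-reduction (RRR) (7% absolute) in the restrictive group on the primary outcome", again from 45% at error levels of 5% and 20%, and adds a number needed to treat of 14 or less.

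No section prints the mortality assumed in the restrictive group or the formula used. Randomisation is 1:1 (protocol 3.2) and tests are two-tailed (protocol 10.2; SAP, Statistical analyses). On the primary analysis, protocol 10.2 says "We will perform the primary analyses adjusted for the stratification variables", and the SAP specifies "Logistic regression analysis adjusted for the stratification variables" (site and haematological malignancy or metastatic cancer).

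**The concern.** From a 45% control rate, a 15% relative reduction and a 7-point absolute reduction imply different restrictive-group rates, 38.25% and 38.0%. One sample size cannot give both exactly 80% power. If 777 was worked out from the rounded absolute figure, the power printed beside the relative figure is too high.

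The relative figure is the one the plan treats as its reference effect. The secondary-outcome power (protocol 10.1.2), the text ruling out stopping for futility (protocol 10.2.3, Appendix 4 and the SAP's interim analysis section) and the required information size quoted in the SAP are all expressed as a 15% relative reduction. A reader who takes 15% at face value gets the wrong power. What is at stake is the accuracy of a stated design figure, not the validity of the trial.

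**Working it through.** **Inputs.** Control mortality p1 = 0.45, n = 777 per group, two-sided alpha 0.05 (z = 1.960), power 0.80 (z = 0.842), 1:1 allocation. All come from protocol 10.1.1, 10.2 and 3.2. The sample size text mentions no dropout allowance, so none is used.

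**Two readings of the effect.**
- 7.0 points absolute: p2 = 0.45 − 0.07 = 0.380; relative reduction 0.07/0.45 = 15.56%.
- 15% relative: p2 = 0.45 × 0.85 = 0.3825; absolute reduction 6.75 points.

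**Formulas** (normal approximation, pooled variance under the null, no continuity correction). With d = p1 − p2, p̄ = (p1 + p2)/2, A = √[2p̄(1 − p̄)] and B = √[p1(1 − p1) + p2(1 − p2)]:
- n per group = (1.960·A + 0.842·B)² / d²
- power = Φ[(d√n − 1.960·A)/B]

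**Reproducing the plan's figure (45% vs 38.0%).** A = 0.6968, B = 0.6951.
- n = (1.3657 + 0.5850)²/0.07² = 3.805/0.0049 = 776.6, so 777 per group and 1554 in total, as printed.
- Power at 777 = Φ[(0.07 × 27.875 − 1.3657)/0.6951] = Φ(0.842) = 80.0%.

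**The same formula for an exact 15% relative reduction (45% vs 38.25%).** A = 0.6971, B = 0.6955.
- n = (1.3663 + 0.5853)²/0.0675² = 3.809/0.004556 = 836.0 per group, 1672 in total, 118 more than planned.
- Power at 777 = Φ[(0.0675 × 27.875 − 1.3663)/0.6955] = Φ(0.741) = 77.1%, a type 2 error of 22.9%.

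The smallest reduction with 80% power at 777 per group is 6.998 points, or 15.55% of 45%.

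**Does the choice of method matter?** Power at 777 per group:

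| Method (two-sided) | 45% vs 38.0% | 45% vs 38.25% |
|---|---|---|
| Pooled normal | 80.0% | 77.1% |
| Unpooled normal | 80.2% | 77.2% |
| Arcsine | 80.0% | 77.1% |
| Chi-square, exact enumeration | 79.9% | 76.9% |
| Continuity-corrected | 78.5% | 75.5% |
| Fisher's exact | 78.5% | 75.3% |
| Pooled, final alpha 0.049 (assumed, for the interim look) | 79.8% | 76.8% |

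No two-sided method gives 80% for an exact 15% reduction. A one-sided 5% test would give 85.5%, but the plan is two-tailed.

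**Adjustment for the stratification variables.** If they explain a share R² of outcome variance, treat the gain as an effective sample size of 777/(1 − R²). Reaching 80% at an exact 15% reduction then needs R² = 1 − 777/836.0 = 7.1%. The documents give no value for R², so what follows is assumption.
- *Cancer alone.* It carries 7 points in the mortality score of protocol Appendix 6. Going from a score of 22 to 29 moves predicted mortality from 40.1% to 63.4%, a log odds ratio of 0.95. With an assumed prevalence of 5% to 25%, R² is 1.1% to 4.1% and power is 77.5% to 78.8%.
- *Cancer and site.* Simulations compared adjusted with unadjusted logistic regression on the same data (4,000 trials per setting). They assumed cancer prevalence of 10% to 25%, 30 sites and a between-site SD of 0 to 0.4 on the logit scale. Adjustment added 1.3 to 2.8 points, giving about 78% to 80%.

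**Scale against the control rate.** Protocol 1.1 says: "Patients with septic shock have 90-day mortality rates around 40% to 50" percent. Unadjusted power for an exact 15% reduction is 69% at a control rate of 40%, 77% at 45% and 84% at 50%.

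**The case against.** The best defence is rounding. The documents give whole percentages, and 6.75 rounds to 7, so the pair is a fair description of one effect at the precision used. That holds for the label. It does not hold for the power, because 777 is the answer for 7.0 points and 6.75 points would need 836.

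The second defence is that the planned primary analysis is adjusted, and under favourable assumptions its power for an exact 15% reduction comes close to 80%. This stands in part, and the 77% must be read as unadjusted. But the sample size text claims no gain from adjustment, and 777 is exactly the unadjusted answer for 7.0 points. Adjustment would also raise the power for 7.0 points, so the two effects still would not share one power.

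Three further objections have some force:
- That 7.0 points sized the trial is an inference, since no restrictive-group rate is printed. The exact match at 777 supports it, as does the number needed to treat of 14 (1/0.07 = 14.3, against 1/0.0675 = 14.8).
- The protocol's named unadjusted test is Fisher's exact, whose power is about 1.5 to 1.8 points lower at both effects. It is not the primary analysis, but corrected wording should name the normal approximation.
- The SAP's summary of changes dates the final analyses to March 2022, so a correction now clarifies the record and cannot affect conduct.

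**Conclusion.** The statement is wrong as written, to a minor degree. At 2 x 777, two-sided 5% and 45% control mortality, the unadjusted power is 80.0% for 7.0 points (15.6% relative) and 77.1% for an exact 15% relative reduction, a gap of 2.9 points. The sample size is correct for the absolute figure, and the trial is not mis-sized.

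The unadjusted result rests only on figures printed in the documents and the standard normal approximation. How much of the gap the adjusted primary analysis closes depends on cancer prevalence and between-site variation, which the documents do not give. The gap is also smaller than the 69% to 84% spread produced by the plan's own range of control mortality.

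**What to change.** In protocol 10.1.1, the protocol abstract and the SAP's sample size section, replace the single power statement with one along these lines: 2 x 777 gives 80% power for a 7.0-point absolute reduction (45% vs 38.0%, a 15.6% relative reduction) and about 77% for an exact 15% relative reduction (45% vs 38.25%), for an unadjusted comparison by normal approximation; the primary analysis adjusts for the stratification variables, so its power may be somewhat higher.

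Leave the sample size, the analysis, the stopping rules and the number needed to treat as they are. The cost is one sentence in three places, with no extra patients and no new analysis. The stated power for the 15% relative effect becomes about 3 points less favourable.
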